5.4.3.2 Abortions

A spontaneous abortion should be classified as a serious adverse event (as the Sponsor considers abortions to be medically significant), recorded on the Adverse Event eCRF, and reported to the Sponsor immediately (i.e., no more than 24 hours after learning of the event; see Section [5.4.2](#)).

If a therapeutic or elective abortion was performed because of an underlying maternal or embryofetal toxicity, the toxicity should be classified as a serious adverse event, recorded on the Adverse Event eCRF, and reported to the Sponsor immediately (i.e., no more than 24 hours after learning of the event; see Section [5.4.2](#)). A therapeutic or elective abortion performed for reasons other than an underlying maternal or embryofetal toxicity is not considered an adverse event.

All abortions should be reported as pregnancy outcomes on the paper Clinical Trial Pregnancy Reporting Form.

5.4.3.3 Congenital Anomalies/Birth Defects

Any congenital anomaly/birth defect in a child born to a female patient exposed to study drug should be classified as a serious adverse event, recorded on the Adverse Event eCRF, and reported to the Sponsor immediately (i.e., no more than 24 hours after learning of the event; see Section 5.4.2).

5.5 FOLLOW-UP OF PATIENTS AFTER ADVERSE EVENTS

5.5.1 Investigator Follow-Up

The investigator should follow each adverse event until the event has resolved to baseline grade or better, the event is assessed as stable by the investigator, the patient is lost to follow-up, or the patient withdraws consent. Every effort should be made to follow all serious adverse events considered to be related to study drug or trial-related procedures until a final outcome can be reported.

During the study period, resolution of adverse events (with dates) should be documented on the Adverse Event eCRF and in the patient's medical record to facilitate source data verification.

All pregnancies reported during the study should be followed until pregnancy outcome.

5.5.2 Sponsor Follow-Up

For serious adverse events, adverse events of special interest, and pregnancies, the Sponsor or a designee may follow up by telephone, fax, email, and/or a monitoring visit to obtain additional case details and outcome information (e.g., from hospital discharge summaries, consultant reports, autopsy reports) in order to perform an independent medical assessment of the reported case.

5.6 ADVERSE EVENTS THAT OCCUR AFTER THE ADVERSE EVENT REPORTING PERIOD

At the time of study treatment completion or study treatment discontinuation, the investigator should instruct each patient to report to the investigator any subsequent adverse events that the patient's personal physician believes could be related to prior study drug treatment or study procedures.

The Sponsor should be notified if the investigator becomes aware of any serious adverse event that occurs after the end of the adverse event reporting period (defined as 28 days after the last dose of study drug), if the event is believed to be related to prior study drug treatment. These events should be reported through use of the Adverse Event eCRF. However, if the EDC system is not available, the investigator should report these events directly to the Sponsor or its designee, either by faxing or by scanning and emailing the paper Clinical Trial Serious Adverse Event/Adverse Event of Special Interest Reporting Form using the fax number or email address provided to investigators.

5.7 EXPEDITED REPORTING TO HEALTH AUTHORITIES, INVESTIGATORS, INSTITUTIONAL REVIEW BOARDS, AND ETHICS COMMITTEES

The Sponsor will promptly evaluate all serious adverse events and adverse events of special interest against cumulative product experience to identify and expeditiously communicate possible new safety findings to investigators, IRBs, ECs, and applicable health authorities based on applicable legislation.

To determine reporting requirements for single adverse event cases, the Sponsor will assess the expectedness of these events using the following reference documents:

Drug	Document
Fulvestrant	Fulvestrant Summary of Product Characteristics
Venetoclax plus fulvestrant combination	Venetoclax Investigator's Brochure for solid tumour studies

The Sponsor will compare the severity of each event and the cumulative event frequency reported for the study with the severity and frequency reported in the applicable reference document.

Reporting requirements will also be based on the investigator's assessment of causality and seriousness, with allowance for upgrading by the Sponsor as needed.

6. STATISTICAL CONSIDERATIONS AND ANALYSIS PLAN

Analysis populations are defined as follows:

- The ITT population is defined as all randomized patients whether or not they were assigned to the arm where the study treatment was administered.
- The BCL-2 high population (patients within ITT and with $\geq 50\%$ of tumor cells stained with an intensity of IHC 2⁺ or 3⁺) or BCL-2 low population (patients within ITT and with BCL-2 $\geq 50\%$ stained with an intensity of IHC 0 or 1⁺ and $< 50\%$ stained an intensity of IHC 2⁺ or 3⁺).
- The safety-evaluable population is defined as patients who received any amount of any component of the investigational or non-investigational study treatments.

The ITT population is the primary analysis population for the study.

6.1 DETERMINATION OF SAMPLE SIZE

Approximately 100 patients need to be recruited and randomized in a 1:1 ratio to two treatment arms (venetoclax + fulvestrant and fulvestrant). The study will enroll both BCL-2 high ($\geq 50\%$ of tumor cells stained with an intensity of IHC 2⁺ or 3⁺) and low

($\geq 50\%$ of tumor cells stained with an intensity of IHC 0 or 1+ and $< 50\%$ IHC 2+ or 3+) patients, and it is planned to enroll approximately 50 BCL-2-high patients.

The sample size of 100 patients provides precision of 15% for 80% CI when calculating the absolute difference in the CBR between the two arms assuming the expected observed CBR in the control arm is 40% (Cristofanilli et al. 2016) and in the venetoclax arm is 60% (i.e., the 80% CI for difference in CBR is from 5% to 35%).

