Necessary supportive measures for optimal medical care will be given throughout the study according to institutional standards, including the use of growth factors (e.g., erythropoietin) if clinically indicated. Granulocyte stimulating factor (G-CSF) will be administered for neutropenia as indicated. At the discretion of the investigator, a prophylactic oral agent (e.g., allopurinol 300 mg QD) may be initiated in patients who are deemed to be at the risk of tumor lysis syndrome (TLS) in order to reduce the uric acid level.

Statistical Methods

Primary Analysis

The primary efficacy endpoint is clinical benefit, defined as complete response (CR), partial response (PR), or stable disease (SD) lasting ≥ 24 weeks from randomization in patients with measurable disease at baseline, as determined by the investigator according to RECIST v1.1. Patients with no response assessments for any reason will be considered non-responders.

The clinical benefit rate (CBR) analysis will be conducted for the intent-to-treat (ITT) population, the BCL-2 high subgroup, and the BCL-2 low subgroup. The confidence intervals for the difference in CBR between the two treatment arms will be determined using the normal approximation to the binomial distribution. An estimate of the CBR and its 95% CI will be calculated for each treatment arm.

Determination of Sample Size

Approximately 100 patients need to be recruited and randomized in a 1:1 ratio to two treatment arms (venetoclax + fulvestrant and fulvestrant). The study will enroll both BCL-2 high ($\geq 50\%$ of tumor cells stained with an intensity of IHC 2+ or 3+) and low ($\geq 50\%$ of tumor cells stained with an intensity of IHC 0 or 1+ and $< 50\%$ IHC 2+ or 3+) patients, and it is planned to enroll approximately 50 BCL-2-high patients.

The sample size of 100 patients provides precision of 15% for 80% CI when calculating the absolute difference in the CBR between the two arms assuming the expected observed CBR in the control arm is 40% and in the venetoclax arm is 60% (i.e., the 80% CI for difference in CBR is from 5% to 35%).

Interim Analyses

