4.2 METHOD OF TREATMENT ASSIGNMENT

After written informed consent has been obtained, all screening procedures and assessments have been completed, and eligibility has been established, the study site will enter demographic and baseline characteristics in the interactive voice or web-based response system (IxRS). For those patients who are eligible for enrollment, the study site will obtain the patient's identification number and treatment assignment from the IxRS.

Randomization will be conducted using a permuted block randomization method through the IxRS. Patients will be randomized into one of the two treatment arms in a 1:1 ratio based on the following stratification factors:

- BCL-2 status: high ($\geq 50\%$ IHC 2+ or 3+) versus low ($\geq 50\%$ IHC 0 or 1+ and $< 50\%$ IHC 2+ or 3+). It is planned to enroll approximately 50 BCL-2-high patients.
- Number of prior therapy in the locally advanced/metastatic setting: one versus two

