6.4.1 Primary Efficacy Endpoint

The primary efficacy endpoint is clinical benefit, defined as CR, partial response (PR) or SD lasting ≥ 24 weeks from randomization in patients with measurable disease at baseline, as determined by the investigator according to RECIST v1.1. Patients with no response assessments for any reason will be considered non-responders.

The CBR analysis will be conducted for the ITT population, the BCL-2 high subgroup, and the BCL-2 low subgroup. The CIs for the difference in CBR between the two treatment arms will be determined using the normal approximation to the binomial distribution. An estimate of the CBR and its 95% CI will be calculated for each treatment arm.

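### Is the stated precision of 15 points for the 80% CI on the CBR difference wrong for 100 patients?

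*Combined protocol and SAP*

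**What the plan says.** The sample-size section of the protocol (6.1) plans about 100 patients, randomized 1:1, with assumed clinical benefit rates of 40% on fulvestrant and 60% on venetoclax plus fulvestrant. Its only quantitative justification is this: "The sample size of 100 patients provides precision of 15% for 80% CI when calculating the absolute difference in the CBR" between the two arms. In brackets it spells out the result: "the 80% CI for difference in CBR is from 5% to 35" percent. The synopsis repeats the claim ("The sample size of 100 patients provides precision of 15% for 80% CI").

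The analysis section for the primary endpoint (6.4.1) fixes the method: "The CIs for the difference in CBR between the two treatment arms will be determined using the normal approximation to the binomial distribution". It gives no confidence level for that difference. The one level it names, 95%, is attached to the rate in each arm. No section mentions a continuity correction. Section 6.4.2.2 carries the same analyses over to objective response rate, and 6.4.1 applies them to the BCL-2 high and low subgroups.

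**The concern.** Most statisticians would check the 15 points with the simplest formula, z times the unpooled standard error, and would get 12.6. The gap of 2.4 points is too large to be rounding at that stage. Read this way, 15 points would be an 87% interval at the planned size, or an 80% interval from about 70 patients. Either would suggest a wrong number or a wrong sample size.

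Precision is the whole case for 100 patients, since the plan states no power and no alpha. If the figure were wrong, the design would have no correct justification. The missing level in 6.4.1 adds to the worry. A reader could carry the 95% across from the per-arm rates to the difference and obtain an interval noticeably wider than the one the design was built on.

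**Working it through.** **Inputs**
- Patients: 100 in total (6.1), allocated 1:1 (4.2 and 6.1), so n = 50 per arm.
- Rates: 40% and 60% (6.1), a difference of 20 points.
- Level: two-sided 80% (6.1), z = 1.2816.
- Method: normal approximation (6.4.1).
- Missing response data: counted as non-response (6.4.1), so n is not reduced.

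**1. Reproducing the plan's figure**

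Standard error = √(0.4 × 0.6/50 + 0.6 × 0.4/50) = √0.0096 = 0.09798.

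Continuity correction = ½ × (1/50 + 1/50) = 0.02.

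Half-width = 1.2816 × 0.09798 + 0.02 = 0.1256 + 0.02 = 0.1456.

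Interval = 20 ± 14.6 points = 5.4% to 34.6%. In whole numbers this is 15, 5 and 35, as printed. A pooled variance with the same correction gives 0.1282 + 0.02 = 0.1482, or 5.2% to 34.8%, which rounds to the same values.

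**2. The uncorrected version**

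Half-width = 1.2816 × 0.09798 = 0.1256, giving 7.4% to 32.6%.

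- Level at which the uncorrected half-width is 15 points: 0.15/0.09798 = 1.531, a two-sided level of 87.4%.
- Patients per arm for 15 points at 80%: 1.2816² × 0.48/0.15² ≈ 35, about 70 in total.

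**3. Sample size with the correction**

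Half-width(n) = 1.2816 × √(0.48/n) + 1/n.

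| n per arm | Total | Half-width |
|---|---|---|
| 47 | 94 | 0.1508 |
| 48 | 96 | 0.1490 |
| 50 | 100 | 0.1456 |

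Fifteen points therefore needs 48 per arm, 96 in total, which fits a plan for approximately 100.

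**4. Effect of the level at the planning rates, 50 per arm**

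| Level | Uncorrected | Corrected |
|---|---|---|
| 80% | ±12.6 (7.4% to 32.6%) | ±14.6 (5.4% to 34.6%) |
| 95% | ±19.2 (0.8% to 39.2%) | ±21.2 (−1.2% to 41.2%) |

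**5. Patients actually enrolled**

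Section 1.4 reports 103 patients, with 19 deaths (37.3%) and 9 deaths (17.3%). This implies 19/0.373 ≈ 51 and 9/0.173 ≈ 52 per arm. At the planning rates the 80% half-width is 12.4 points uncorrected and 14.3 corrected. Both are within the stated 15.

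**The case for a change.** The best case for a change does not rest on the arithmetic. It is that the primary contrast cannot be reproduced from 6.4.1 alone, because neither the level nor the correction is written there. The level is not trivial: with the correction that recovers the printed figure, the 80% interval at the planning rates excludes zero and the 95% interval does not. The correction grows in the subgroups. With about 50 BCL-2-high patients, or 25 per arm, it is ½ × (1/25 + 1/25) = 4 points, taking the 80% half-width from 17.8 to 21.8. The summary of changes also says Version 4 revised this section to add the 95% interval for the rate, yet the difference was left without a level.

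All of this is accurate, and a sentence on each detail would have been better drafting. It falls short of requiring a change for three reasons.
- The level is not absent from the plan. Section 6.1 and the synopsis attach 80% to the difference in CBR by name, and the 95% in 6.4.1 is tied to each arm.
- Whether an interval crosses zero triggers nothing. There is no test and no go/no-go threshold, and 6.9 calls the study hypothesis-generating.
- Version 4 postdates the read-out of the primary analysis, which showed no numerical improvement in CBR (1.4). Settling the level or the correction at this point would be done with the results known and would no longer serve as pre-specification.

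**Conclusion.** The printed precision is not shown to be an error. It follows, to the whole numbers the plan uses, from a continuity-corrected normal approximation with 50 per arm, and that is one form of the method named in 6.4.1. That the sponsor used this correction is an inference from the match on all three figures and from the 96-patient requirement; the documents do not say so.

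The conclusion does not depend on that inference. If the correction was not intended, the 80% interval is 2.4 points narrower on each side than stated (12.6 against 15), so the plan understates its precision and 100 patients remain enough. Replacing the figure with 12.6 could put a number from a different method in place of one that reproduces.

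What remains is incomplete detail: the level for the difference is given in the sample-size text but not repeated in 6.4.1, and the correction is unstated. An analyst following the plan would report the difference at the 80% design level, label any 95% interval as additional, and note whether a correction was applied. That gives sound results. This rests on 1:1 allocation, the planning rates of 40% and 60%, and the absence of any decision rule tied to a confidence limit.

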6.2 SUMMARIES OF CONDUCT OF STUDY

Patient enrollment, duration of follow-up, and discontinuation from the study and reasons for discontinuation will be summarized by treatment arm for all randomized patients. In addition, major protocol violations will be summarized by treatment arm.

6.3 SUMMARIES OF DEMOGRAPHIC AND BASELINE CHARACTERISTICS

Demographic and baseline characteristics (including age, sex, race, lines of prior therapy in the locally advanced/metastatic setting, BCL-2 status, sites of disease [bone vs. nodal vs. visceral], previous endocrine therapy type [AI vs. tamoxifen vs. combination], menopausal status [pre-/perimenopausal vs. postmenopausal]), will be summarized using means, standard deviations, medians, and ranges for continuous variables and proportions for categorical variables, as appropriate. Summaries will be presented overall and by treatment group.

6.4 EFFICACY ANALYSES

Patients will be analyzed in accordance with the treatment arm to which they were randomized.

The primary analysis will be conducted when all patients have discontinued from study treatment, or 6 months after last patient in, whichever occurs first.

6.4.1 Primary Efficacy Endpoint

The primary efficacy endpoint is clinical benefit, defined as CR, partial response (PR) or SD lasting ≥ 24 weeks from randomization in patients with measurable disease at baseline, as determined by the investigator according to RECIST v1.1. Patients with no response assessments for any reason will be considered non-responders.

The CBR analysis will be conducted for the ITT population, the BCL-2 high subgroup, and the BCL-2 low subgroup. The CIs for the difference in CBR between the two treatment arms will be determined using the normal approximation to the binomial distribution. An estimate of the CBR and its 95% CI will be calculated for each treatment arm.

6.4.2 Secondary Efficacy Endpoints

6.4.2.1 Progression-Free Survival

PFS is defined as the time from randomization to the first occurrence of disease progression (as determined by the investigator according to RECIST v1.1) or death from any cause, whichever occurs first. Data for patients without the occurrence of disease progression or death as of the clinical data cut-off date will be censored at the time of the last tumor assessment (or at the time of randomization plus 1 day if no tumor assessment was performed after the baseline visit).

The Kaplan-Meier approach will be used to estimate median PFS for each treatment arm. The Cox proportional hazards model and its 95% CI, stratified by lines of prior therapy (one vs. two) and BCL-2 status (high vs. low), will be used to estimate the hazard ratio between the two treatment arms. The unstratified hazard ratio will also be provided.

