- **Control arm:** fulvestrant 500 mg administered as two 250-mg IM injections on Cycle 1 Days 1 and 15, and then on Day 1 of each subsequent 28-day cycle. No crossover to the venetoclax arm is permitted.

Tumor assessments will be conducted for all patients at screening and at every 8 weeks (± 5 days) from the date of randomization until Week 24 (± 5 days) and every 12 weeks (± 5 days) thereafter. Tumor assessments will be conducted regardless of dose delays or early discontinuation, until investigator-assessed disease progression (as specified below), the predefined end of the study (Section 3.3), or until death, whichever occurs first.

Study treatment for each patient will continue until disease progression, unacceptable toxicity, withdrawal of consent, death, or study termination by the Sponsor, whichever occurs first.

Diagnosis of disease progression should be supported by radiology assessments as per RECIST v1.1. All patients who are discontinued from all study treatment will return for a study drug discontinuation visit 28 days (+3 days) after the last dose of study treatment.

Patients who are discontinued from study treatment for reasons other than disease progression and have started follow-on treatment will be followed for survival approximately every *3 months, or more frequently*, until death, loss to follow-up, withdrawal of consent, or study termination by the Sponsor, whichever occurs first.

Patients who are discontinued from study treatment for reasons other than disease progression and have not started follow-on treatment will be followed for disease status every 8 weeks (± 5 days) from the date of randomization until Week 24 (± 5 days) and then every 12 weeks (± 5 days) thereafter until disease progression, death, loss to follow-up, withdrawal of consent, or study termination by the Sponsor, whichever occurs first.

[figure not shown]
After disease progression, patients will be followed for survival and subsequent anti-cancer therapies approximately every *3 months, or more frequently*, until death, loss to follow-up, withdrawal of consent, or study termination by the Sponsor, whichever occurs first.

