4.5.5 Tumor and Response Evaluations

All known sites of disease must be assessed per RECIST v1.1 and documented at screening (within 28 days prior to Cycle 1 Day 1) and re-assessed at each subsequent tumor evaluation (every 8 weeks [± 5 days] from the date of randomization until Week 24 [± 5 days] and every 12 weeks [± 5 days] thereafter). Tumor assessments should be performed on this schedule regardless of dose delay until disease progression. In case of early discontinuation, only the patients who discontinue study treatment early without progression and who have not started follow-on treatment will remain on the study's schedule of assessments for progression. Patients who progress or discontinue early without progression but who have initiated a new treatment will remain on the study for OS.

Screening assessments must include computed tomography (CT)/magnetic resonance imaging (MRI) scans of the chest, abdomen, and pelvis; CT/MRI scans of the neck and brain imaging should be included if clinically indicated. A documented SOC tumor assessment performed within 28 days prior to Cycle 1 Day 1 may be used for the

screening assessment provided it meets the above requirements. CT scans should be performed with a contrast agent. For patients with known allergies to the contrast media, it is acceptable to perform a chest CT scan without contrast and an MRI scan for the abdomen (ideally at baseline and every tumor assessment thereafter).

If a CT scan for tumor assessment is performed in a positron emission tomography (PET)/CT scanner, the CT acquisition must be consistent with the standards for a full-contrast diagnostic CT scan.

Response assessment will be made by the investigator on the basis of physical examinations, CT scans, or MRI, and/or bone scans using criteria outlined in RECIST v1.1 ([Appendix 4](#)). The same radiographic procedure used to assess disease sites at screening should be used throughout the study (e.g., the same contrast protocol for CT scans). Assessments should be performed by the same evaluator to ensure internal consistency across visits.

CT scans throughout the study should include chest, abdomen, and pelvic scans. CT scans of the neck and brain imaging should be included if clinically indicated. At the investigator's discretion, CT scans may be repeated at any time if progressive disease (PD) is suspected.

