4.5.5.2 Tumor Scans

To ensure a valid comparison of tumor data and uniformity in the assessment of tumor response during the study, the following procedures must be implemented at the study site:

- All lesions identified at baseline (target and non-target) will be reassessed using the same method throughout the course of the study.
- All CT scans and MRIs obtained for all patients enrolled at the center should be reviewed by the local radiologist who, together with the investigator, will determine the local assessment of response and progression. All bone scans obtained from the patient with bone metastases at baseline also should be reviewed similarly.
- For patients with measurable disease at baseline, tumor response and progression will be determined by the investigator according to RECIST v1.1 criteria and will be the basis for the efficacy analyses.

Only the patients who discontinue study treatment early without progression and who have not started follow-on treatment will continue to undergo tumor-response evaluations until PD.

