5.3.5.10 Lack of Efficacy or Worsening of Metastatic Breast Cancer

Events that are clearly consistent with the expected pattern of progression of the underlying disease should not be recorded as adverse events. These data will be captured as efficacy assessment data only. The expected pattern of progression will be supported by radiology assessments as per RECIST v1.1. In rare cases, the determination of clinical progression will be based on symptomatic deterioration. However, every effort should be made to document progression through use of objective criteria. If there is any uncertainty as to whether an event is due to disease progression, it should be reported as an adverse event.

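### Does stopping scans at new therapy, then censoring PFS at the last scan, call for a different PFS analysis?

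*Combined protocol and SAP*

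**What the plan says.** - **PFS event and censoring (Section 6.4.2.1).** The event is investigator-assessed RECIST v1.1 progression or death from any cause. Everyone else "will be censored at the time of the last tumor assessment (or at the time of randomization plus 1 day" if there was no scan after baseline. New anti-cancer therapy is not mentioned, so a death after a switch counts on its own date. Planned outputs are Kaplan-Meier medians and stratified and unstratified Cox hazard ratios.
- **Scans off treatment (Sections 4.5.5 and 4.5.5.2).** Only patients "who discontinue study treatment early without progression and who have not started follow-on treatment will remain on the" assessment schedule. Section 4.5.5.2 repeats that only early stoppers "who have not started follow-on treatment will continue to undergo tumor-response evaluations until PD".
- **The same point in Section 3.1.** A general sentence reads "Tumor assessments will be conducted regardless of dose delays or early discontinuation, until investigator-assessed disease progression". Later in the section, patients who stop for reasons other than progression "and have started follow-on treatment will be followed for survival".
- **Unscanned worsening.** Section 4.5.5.1 and Appendix 4 do not treat symptomatic deterioration without imaging as progression. Section 5.3.5.10 says "In rare cases, the determination of clinical progression will be based on symptomatic deterioration", and that "every effort should be made to document progression through use of objective criteria". Section 4.5.5 adds that "CT scans may be repeated at any time if progressive disease (PD) is suspected".
- **Related outputs.** Section 6.2 tabulates discontinuation from the study by arm. Section 6.5 covers adverse events leading to drug discontinuation or interruption. Neither counts new therapy before progression.
- **Duration of response (Section 6.4.2.3).** The censoring rule is the same, with Kaplan-Meier estimates in responders only.

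**The concern.** Censoring at the last scan is harmless when the reason a patient leaves scanning is unrelated to prognosis. A patient who feels worse, stops treatment and starts another drug before a scan confirms progression is the opposite case: the true event has happened, and the rule either drops it or postpones it to death. The arm with more of these patients looks better than it is. More such switching on venetoclax lowers the hazard ratio; more on control raises it.

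The trial is open-label, so the willingness to switch could well differ by arm. A reader of the PFS result could not tell whether it had, because no planned output reports new therapy before documented progression, censoring reasons by arm, or a PFS sensitivity analysis. At stake is the credibility of the PFS hazard ratio, which Section 1.4 cites in its benefit-risk summary. Overall survival is unaffected, because it does not depend on scans.

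**Working it through.** **No PFS figure to reproduce.** Section 6.1 sizes the trial on the precision of the clinical benefit difference. It gives no PFS median, hazard ratio, event count or switching rate, so the shift can only be illustrated under assumptions.

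**Inputs from the documents.** Scans every 8 weeks to Week 24, then every 12 weeks (Section 3.1). Enrolment of about 18 months (Section 3.3) and analysis 6 months after the last patient in (Section 6.4) give follow-up of roughly 6-24 months. Arms of 51 and 52 follow from 19/51 = 37.3% and 9/52 = 17.3% (Section 1.4).

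**Assumptions.**
- Simulation A: exponential PFS with median 12, 20 or 36 weeks; exponential post-progression survival with mean 30, 60 or 100 weeks; true hazard ratio 1.0.
- Simulation B: control median PFS 2.5, 4 or 6 months; median post-progression survival 8 or 18 months; true hazard ratio 1.0 or 0.75. Results are the planned hazard ratio divided by the one obtained with scans continued.
- Both use an unstratified Cox model. The percentages are patients who switch because of progression that is never imaged.

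| Undocumented switching, venetoclax vs control | A: hazard ratio | B: ratio |
|---|---|---|
| 5% vs 2% | 0.97-0.98 | – |
| 2% vs 5% | 1.01-1.03 | – |
| 10% vs 5% | – | 0.95-0.97 |
| 5% vs 10% | – | 1.03-1.06 |
| 15% vs 5% | 0.90-0.95 | 0.91-0.94 |
| 5% vs 15% | 1.05-1.10 | 1.06-1.11 |
| 20% vs 5% | – | 0.87-0.91 |
| 25% vs 5% | – | 0.83-0.88 |
| Equal | 0.99-1.01 (5% each) | 1.00; at most 1.02 at true hazard ratio 0.75 |

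In patients: 0.05 × 51 = 2.6 and 0.02 × 52 = 1.0, about 3 versus 1. Likewise 0.15 × 51 = 7.7 and 0.05 × 52 = 2.6, about 8 versus 3.

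**Scale of the uncertainty.** If all 103 patients had a PFS event, the standard error of the log hazard ratio would be about 2/√103 = 0.197. The 95% CI around 1.0 is then exp(±1.96 × 0.197), or 0.68-1.47. With 60-95 events the interval is a factor of about 1.5-1.7 either way. A 1-3% shift is lost in that, and even 25% versus 5% stays inside it.

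**Would another rule do better?** Simulation A, true hazard ratio 1.0. The mixed case has 15% toxicity-driven plus 5% disease-driven switching on venetoclax, and 15% disease-driven on control.

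| Rule | Mixed case | Across scenarios |
|---|---|---|
| Planned | 1.06-1.10 | 0.90-1.10 |
| All new therapy counted as an event | 1.06-1.19 | 0.97-1.20 |
| Censor at last scan before new therapy | 1.10-1.12 | 0.90-1.12 |
| Event only if the reason is disease-related, coded correctly | 0.96-1.02 | 0.96-1.03 |
| Same, 20% of reasons miscoded in both arms | – | 0.99-1.07 |
| Same, 40% of reasons miscoded differently by arm | 0.94-1.15 | 0.94-1.15 |

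The first two alternatives do not improve on the plan's worst error. The reason-based rule improves on it when reasons are coded well, and can lose to it (1.15 versus 1.10) when coding differs by arm.

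**The case for a change.** The strongest argument for acting is that the gap is real and cheap to close. No text handles new therapy before progression, the two simulations agree where they overlap, and the reason-based rule is clearly better when reasons are accurate (0.96-1.02 against 1.06-1.10 in the mixed case). The primary reason for stopping is already recorded (Section 4.6.1). From 8 October 2020 only one arm was asked to stop a study drug, which could make switching differ by arm in later updates of PFS.

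Part of this stands. The mechanism, the either-way direction and the missing count are correct, and imbalances of 15-20 points would produce shifts that are not negligible.

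The case for a new analysis is weaker:

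- The reason-based rule would count symptomatic deterioration as an event, which Section 4.5.5.1 excludes from efficacy analyses.
- It needs one primary reason per patient, judged open-label. Section 4.6.1 would let a site record a disease-driven switch as use of another anti-cancer therapy or as the patient's best interest. Arm-dependent judgement is the problem it is meant to solve.
- Start dates of new therapy may be incomplete at the 5 August 2020 cut-off for patients who stopped without progression. Section 4.6.1 names collection of new therapy only after progression, and the Appendix 1 footnote on reporting it once known came with this later amendment.
- The October 2020 request postdates the primary analysis. Patients could stay on fulvestrant, and so on scans.
- For duration of response no hazard ratio is planned, and no calculation shows a material effect.

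The two scan statements in Section 3.1 are a drafting looseness. The section itself gives the follow-on exception and Section 4.5.5 states it specifically, so the specific rule governs. Any scans a site did obtain after a switch would simply enter the planned rule. The wording can be reconciled whenever the text is next revised.

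**Conclusion.** No change to the plan follows. Section 6.4.2.1 gives a complete, conventional event and censoring rule for a secondary endpoint that is estimated, not tested, in a study Section 6.9 calls hypothesis-generating. At plausible imbalance (5% versus 2%) the shift is 1-3%; at 15% versus 5%, which is high given that Section 5.3.5.10 expects reliance on symptoms to be rare, it is 5-10%. Both are small against a best-case 95% CI of 0.68-1.47. No alternative rule is shown to be better overall.

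This rests on assumed switching rates, medians and survival after progression, none of which the documents give. The observed PFS hazard ratio is not reported either, so it cannot be said whether a shift of a few percent would move it across 1.0. The decision in Section 1.4 does not hang on that: it rests on overall benefit-risk, including 19 versus 9 deaths.

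Analysts can fill the remaining gap in reporting: a by-arm count of patients who began new therapy before documented progression, with the reason for stopping and whether each was censored or died, labelled post hoc for the August 2020 cut-off. Low or balanced counts would largely settle the question.
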